Outcome Adjudication: The DCC will direct the adjudication of study outcomes. Assigning cause-specific mortality, as is required for the primary VEST outcome and a number of important secondary endpoints for VEST, can be difficult. Cardiac electrophysiologists actively engaged in clinically relevant patient care will be employed to provide expert opinions regarding these endpoints. The Endpoints Director will manage the adjudication process designed to categorize arrhythmias and deaths appropriately, minimize bias by blinding adjudicators to treatment assignment, and protect against unnecessary disclosure of protected health information. Table 3 lists the primary and secondary outcomes, the data source, and whether or not each endpoint requires adjudication. Definitions for each endpoint are provide below.

Cause-specific Mortality and Non-Fatal Cardiovascular Events: Deaths will be reported by family members or clinicians, or detected by clinical sites when study participants fail to show up for scheduled examinations or miss scheduled data transmissions. Social security death index searches will be performed for all participants lost to follow-up for whom vital status is unknown in the U.S.. Hospitalizations will be reported by participants at or between scheduled examinations or phone calls. Sites will notify the DCC within 48 hours of learning about a death or cardiovascular hospitalization, and will then have eight weeks to obtain a death certificate; all discharge summaries for any hospitalizations occurring within 1 month of the index death/hospitalization, and narratives from personal contacts of deceased participants (listed at recruitment) regarding manner and circumstances of death. All personal identifiers and mention of treatment assignment (for the VEST arm) will be carefully stripped by clinical site staff to the extent possible. For all deaths, the DCC will redact any mention of the LifeVest in participants assigned to VEST, and add fake redaction in participants assigned to NO VEST so that adjudication of cause of death will be blinded. ECG data from the LifeVest will NOT be used to adjudicate fatal outcomes for VEST,

Protocol

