because this information will not be available on participants without a LifeVest, and use might induce bias from differential measurement error. Complete packets will be assembled by the DCC and read independently by two adjudicators. Every death will be categorized according to the cause-specific mortality and non-fatal cardiovascular event categories described in Table 3. Disagreements will be resolved by consensus, involving a third adjudicator when required.

Ventricular Arrhythmias: Electronic rhythm strips recorded by the LifeVest will be uploaded to the study database via electronic data transfer from ZOLL. Strips will be presented to adjudicators in batches, with study ID numbers and adjudication forms and read independently by two cardiac electrophysiologists. Adjudicators will determine whether the LifeVest therapy was "appropriate" or "inappropriate" based primarily on the presence or absence of a true ventricular arrhythmia. Discordances will be resolved by consensus, involving a third adjudicator when required.

Quality of Life: Quality of life outcomes will be measured using self-administered questionnaires mailed to participants 1-2 weeks prior to the 3 month visit. QOL will be assessed using the SF-36 for health related quality of life, the CES-D to measure depression, the Spielberger STAI to measure anxiety, and the MOS sleep scale to measure sleep patterns. The EQ-5D will be administered to measure subjective health status, and the International Physical Activity Questionnaire (IPAQ) short format for physical activity. The Florida Patient Acceptance Scale (FPAS) will be included to measure device acceptance in those randomized to the LifeVest.

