1.5.10 Adverse/Outcome Events

Most symptoms, signs and clinical events will be captured by questionnaire during routine scheduled clinic and telephone visits. Data collection forms are specifically designed to capture known adverse events from the LifeVest including physical discomfort (rash, etc.). Inappropriate shock events will be adjudicated, as above. Site investigators will make a determination for all deaths and hospitalizations about whether the event was related to participation in the study; all such events will be adjudicated and summarized for the Data Safety Monitoring Board (DSMB).

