1.5.11 Analysis Plan for VEST

Treatment effects on the primary outcome, sudden death and death due to ventricular arrhythmia, will be assessed using stratified exact methods to compare cumulative incidence in the VEST and control groups at 60/90 days. An exact test of the primary null hypothesis of no treatment effect will be conducted using a two-sided alpha of 5%. This analysis will be by intention to treat (ITT), without regard to adherence to the assigned study intervention or other aspects of care. The analysis will be jointly

OUTCOMES	PRIMARY/S ECONDARY	DATA SOURCE	ADJUDICATED
Sudden death mortality	Primary	Records/interviews [†]	Yes
All-cause (total) mortality	Secondary	Records/interviews [†]	Yes

VEST	Protocol	1	
Cause-specific mortality			
Non-sudden death	Secondary	Records/interviews [†]	Yes
Ventricular Arrhythmia Death	Primary	Records/interviews [†]	Yes
Other Fatal Arrhythmia	Secondary	Records/interviews [†]	
Non-Sudden Fatal MI	Secondary	Records/interviews [†]	Yes
Fatal Congestive Heart Failure	Secondary	Records/interviews [†]	Yes
Other Cardiac Death	Secondary	Records/interviews [†]	Yes
Fatal Stroke	Secondary	Records/interviews [†]	Yes
Other Non-cardiac Death	Secondary	Records/interviews [†]	Yes
Indeterminate Cause of Death	Secondary	Records/interviews [†]	Yes
Time to death after 1 st VT/VF episode	Secondary	Records/ICD/Reveal	Yes
Non-Fatal Cardiovascular Events			
MI	Secondary	Records/interviews [†]	Yes
Atrial fibrillation	Secondary	Records/interviews [†] / ICD/Reveal	Yes
Congestive heart failure	Secondary	Records/interviews [†]	Yes
Stroke	Secondary	Records/interviews [†]	Yes
LifeVest Events			
Ventricular Tachyarrhythmia	Secondary	LifeVest	Yes
LifeVest Shocks delivered	Secondary	LifeVest	Yes
30 Beats of VT (CL 330-370 msec)	Secondary	LifeVest	Yes
Inappropriate Shock - SVT	Secondary	LifeVest	Yes
Inappropriate Shock - Malfunction	Secondary	LifeVest	Yes
Time to 1 st episode of VT/VF	Secondary	LifeVest	Yes
Adverse Events	-		
Device-attributable Death or Hospitalization	Secondary	Records/interviews [†]	Yes
Device-related Symptom or Sign	Secondary	Data Form	No
Device Change-out	NA	Data Form	No
Other Adverse Event	Secondary	Data Form	No
Vest Compliance	Secondary	LifeVest	
ICD Implantation	Secondary	Data Form	No
Quality of Life	Secondary	QOL Instruments	No
Resource Utilization/Cost	Secondary	Data form	No

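### Does redacting every LifeVest mention from death records make device-attributable death impossible to adjudicate?

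*Combined protocol and SAP*

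**What the plan says.** Table 3 places "Device-attributable Death or Hospitalization" in its adverse-event block as a secondary outcome, adjudicated. Its source is records and interviews, which the table's footnote defines as medical records, death certificates, interviews and National Death Index searches. LifeVest data are not among them.

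Section 1.5.9, in the paragraph on cause-specific mortality and non-fatal cardiovascular events, states: "For all deaths, the DCC will redact any mention of the LifeVest in participants assigned to VEST". Control records receive sham redactions, and the purpose given is blinded adjudication of cause of death. The same paragraph adds: "ECG data from the LifeVest will NOT be used to adjudicate fatal outcomes for VEST". The reason follows: "because this information will not be available on participants without a LifeVest", so that its use could bias the comparison between arms. Two adjudicators read each packet independently, and their task is set out: "Every death will be categorized according to the cause-specific mortality and non-fatal cardiovascular event categories described in Table 3".

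The next paragraph of 1.5.9 deals with arrhythmias: "Electronic rhythm strips recorded by the LifeVest will be uploaded to the study database via electronic data transfer". Two electrophysiologists read the strips and judge whether the therapy was appropriate.

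Section 1.5.10 covers adverse events: "Site investigators will make a determination for all deaths and hospitalizations about whether the event was related to participation in the study". These events are then adjudicated and summarized for the DSMB. Section 1.5.5 says that clinicians are not blinded to assignment.

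**The concern.** The two-reader packet is the only reading of deaths that the protocol describes in detail. A reader confined to it could not attribute a death to the LifeVest. The ECG bar refers to fatal outcomes generally and not to cause of death alone. Section 1.5.9 promises a definition for each endpoint, but none follows for device-attributable death. SAP B.3 plans an analysis of vest-related symptoms and does not name this outcome.

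This is the gravest item in the adverse-event block, and the DSMB receives the adjudicated events. If attribution failed, a count of zero could look reassuring without being informative. A comparison of total mortality between arms would not make up for it, because a handful of extra deaths is far below what such a comparison can detect.

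A smaller worry concerns the definition of sudden death in 1.5.9. It allows device arrhythmia results for unwitnessed deaths without saying which device is meant, shortly before LifeVest ECG is excluded.

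**Working it through.** The question is mainly one of reading, and the plan has no figure of its own to reproduce.

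**1. Scope of the redaction.** It applies to all deaths, but its stated aim is blinded adjudication of cause of death. It stands in the paragraph on cause-specific mortality and cardiovascular events, and the packets are sorted into those categories only. Device-attributable death is under neither heading of Table 3. The packet reading was therefore not described as the place where this outcome is decided.

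**2. Scope of the ECG bar.** Its wording is broad. Its reason is differential measurement between arms, which does not arise for an outcome that concerns the vest itself. Even on the literal reading, the bar removes nothing that the Table 3 row lists as a source, since that row relies on records and interviews.

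**3. The separate route.** Section 1.5.10 requires a site determination for every death and hospitalization, made by people who know the arm and the circumstances. Adjudication follows. This does not settle everything: the site judges relatedness to study participation, which is wider than attribution to the device, and the materials for the later adjudication are not stated.

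**4. Hospitalization.** The outcome is death or hospitalization. The coordinating center's redaction covers deaths and the ECG bar covers fatal outcomes, so neither reaches non-fatal hospitalizations. Inappropriate shocks have their own adjudicated rows, with the LifeVest as source.

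**5. Analysis.** Protocol 1.5.11 includes adverse events among the outcomes to be analyzed and plans exact methods for rare ones. A vest-arm count with an exact interval can be reported from the same data.

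**6. The undefined device.** Table 3 names ICD and Reveal as data sources elsewhere. If the phrase in the sudden-death definition means such implants, it agrees with the LifeVest bar. If it was meant to include the LifeVest, the explicit bar governs.

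**7. What incomplete detection would do.** The inputs are 2300 participants (1.5.12) randomized 2:1 (1.5.6).

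- Vest arm: 2300 × 2/3 = 1533. Control arm: 767.
- One-sided 95% upper limit for zero cases: 1 − 0.05^(1/1533) = 0.195%, or about 3 deaths.
- With an assumed detection share s, the limit is 0.195%/s. With 3 assumed true cases, the chance of finding none is (1 − s)³.

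| Assumed s | Upper limit | Chance of finding none of 3 |
|---|---|---|
| 50% | 0.39% | 12.5% |
| 25% | 0.78% | 42% |
| 10% | 1.95% | 73% |
| 0 | none | 100% |

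For 3 extra vest-arm deaths (3/1533 = 0.20 points), a two-sided 5% comparison of total mortality has 3.7% to 4.7% power in the direction of harm. This assumes control mortality of 6% down to 2% and uses a normal approximation with pooled variance under the null. The documents give no total mortality for this calculation.

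The table shows what a given detection failure would cost. It does not show that there is one: no value of s, and no count of true cases, comes from the documents. It also takes no account of the site determination in step 3.

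**The case for a change.** The strongest case for a change is that Table 3 promises adjudication and not merely a site opinion. On the face of the protocol, that adjudication has no definition, no named reader and no stated material beyond packets that cannot support it. Records and strips are already collected, so a separate unredacted reading after cause of death is locked would need no new data and would protect the blinding of the primary endpoint.

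Much of this stands. The readers and materials are indeed unstated, the site question is not identical to device attribution, and the broad wording of the ECG bar is loose. The weakness of arm-level mortality as a substitute is also real.

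It does not follow that the outcome cannot be judged, or that its count must tend to zero. Both conclusions require the redacted packet to be the only input and the determination under 1.5.10 to be set aside, and no section says either. Nor is there a forced choice between attributing deaths and blinding the primary endpoint, since the order of the readings resolves it. A second panel for all vest-arm deaths would have a cost: at an assumed 2% to 6% mortality, 1533 × 0.02 = 31 to 1533 × 0.06 = 92 deaths, read by assessors outside the cause-of-death panel. The documents do not show that this expense is needed.

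**Conclusion.** No change to the plan follows. The apparent conflict comes from applying rules written for blinded cause of death to an outcome in the adverse-event block that has its own route in 1.5.10. What is left is a gap in described procedure that the data coordinating center can fill sensibly. It can settle cause of death first from the redacted packet, then take device attribution from the site determination and the underlying records. That respects the redaction and the ECG bar and leaves the primary endpoint blinded. The undefined device is an ambiguity that the explicit LifeVest exclusion already resolves.

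No magnitude is claimed, because every figure for missed cases depends on an assumed detection share. The conclusion rests on reading the redaction by its stated purpose and on the 1.5.10 determination being carried forward into adjudication. The Operations Manual, to which the protocol leaves much procedural detail, was not available, so whether it already names the readers and materials could not be checked.

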Blinding to treatment assignment: Participants and clinicians will not be blinded to treatment assignment (LifeVest versus no LifeVest). Since the primary outcome in *VEST* is sudden death and death due to ventricular arrhythmia, it is unlikely that this outcome would be significantly affected by either participant or clinician knowledge of treatment assignment.

Blinding to arrhythmias: Clinicians will be blinded to most arrhythmia recordings from the LifeVest in the group assigned to wear the LifeVest. This is necessary to prevent co-interventions with inappropriate anti-arrhythmic drugs or early implantation of an ICD. There are provisions for unblinding when clinically indicated, as detailed in Chapter 6 of the Operations Manual. Two types of unblinding will occur:

1) Automatic unblinding, generated by the DCC or ZOLL, which will result in electronic notification to the site and sending of LifeVest monitoring strips. Automatic unblinding will be initiated if any of the following events occurs:

- Participant receives a shock
- LifeVest alarms, but participant averts a shock or the rhythm spontaneously terminates if the rhythm lasts > 30 seconds
- Asystole or Bradycardia less than 20 bpm

2) Clinical sites can request unblinding and receive LifeVest strips under the following circumstances:

- Participant suffers a cardiac arrest, or reports receiving a shock or LifeVest alarm
- Participant complains of syncope or pre-syncope
- Participant complains of palpitations
- Physician deems it to be medically necessary (a protocol deviation may be reported)

The procedure for requesting these strips will require a case report form (completed by ZOLL personnel) with a diagnosis or rationale (as outlined above), the date range of strips requested and a follow-up form that documents any treatment changes resulting from viewing these strips.

Crossovers

Participants randomized to the control arm of VEST should not wear a LifeVest during the 3 month VEST follow-up period; use of a LifeVest by a control participant will be recorded as a protocol deviation.

Treatment of Participants Who Receive a LifeVest Shock

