Evaluation and treatment of participants who receive a shock while wearing the LifeVest will be determined by the treating physicians. Recommendations for possible evaluation strategies and treatment will be included in the Operations Manual (Chapter Guidelines for Care of the Medical Treatment). This may include the possibility of assessing for recurrent ischemia, treatment of arrhythmias such as atrial fibrillation or titration of medication.

Early ICD Implantation

It is recognized that some participants will develop indications for ICD implantation during the 3 month VEST portion of the study. Given the short follow-up of only 3 months, we anticipate that this will be a rare event. The protocol provides for participants in the control (non-LifeVest group) and the intervention group (LifeVest group) who suffer an aborted cardiac arrest subsequent to the qualifying

Protocol

MI/hospitalization to be implanted with an ICD. Participants with syncope and >30 seconds of VT may also have an ICD implant.

The following are NOT considered appropriate reasons for early ICD implantation and if elected by the treating physician will be considered protocol deviations:

- Malfunction of the LifeVest (Poor sensing or inappropriate detection/shock delivery)
- Poor participant compliance
- Non-sustained ventricular arrhythmias (<30 seconds)
- Asymptomatic ventricular arrhythmias

In addition, a detailed algorithm for initiation of anti-arrhythmic drugs for ventricular arrhythmias and atrial fibrillation based on ACC/AHA Guidelines will be provided in the operations manual.^{6, 9} Deviations from these algorithms that are elected by the attending physician will be considered a protocol deviation.

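### Central and sham redaction are specified for deaths only, so masking is weaker for adjudicated non-fatal events; for atrial fibrillation, detection may also differ by arm

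*Combined protocol and SAP*

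**What the plan says.** Protocol 1.5.9 (Outcome Adjudication) treats deaths and non-fatal cardiovascular events under one heading and describes four protective steps:

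- **Stripping at the site.** Personal identifiers and mentions of treatment assignment "will be carefully stripped by clinical site staff to the extent possible". This step is not limited to deaths.
- **Central redaction.** "For all deaths, the DCC will redact any mention of the LifeVest in participants assigned to VEST".
- **Sham redaction.** For controls, the DCC will "add fake redaction in participants assigned to NO VEST so that adjudication of cause of death will be blinded".
- **Bar on vest ECG.** "ECG data from the LifeVest will NOT be used to adjudicate fatal outcomes for VEST", because controls have no such recordings and "use might induce bias from differential measurement error".

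Table 3 (in 1.5.11) marks non-fatal MI, AF, heart failure and stroke as adjudicated secondary outcomes. The AF row reads "Atrial fibrillation Secondary Records/interviews" and adds ICD/Reveal; it does not name the LifeVest. The text of 1.5.11 plans treatment-effect analyses of non-fatal cardiovascular events as a class. SAP B.3 compares re-infarctions and hospitalizations between arms.

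Protocol 1.5.5 states that the trial is open label and that clinicians are blinded to most LifeVest rhythm recordings. There are exceptions. Automatic unblinding follows a shock, certain alarms, or asystole or extreme bradycardia, "which will result in electronic notification to the site and sending of LifeVest monitoring strips". Sites may also ask for strips after events such as palpitations, syncope or pre-syncope. Evaluation after a shock may include "treatment of arrhythmias such as atrial fibrillation".

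**The concern.** In an open-label trial, masked adjudication is the main remaining protection for events that need judgement, such as heart failure or re-infarction. For deaths the protocol evidently did not regard site stripping as enough, since it added a central step and a sham step. It gives no reason for stopping there. A vest mention that site staff miss in a non-fatal packet will reach the adjudicators, and nothing in control packets is designed to disguise the difference. A between-arm difference in these outcomes would then be harder to defend.

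AF raises a second question. The protocol's own reason for barring vest ECG for deaths is that only one arm has it. That reason would apply equally to a non-fatal rhythm diagnosis, but no rule says so. If strips seen by the site lead to AF being charted in vest participants, some excess AF in that arm could come from detection alone.

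**Working it through.** The point turns on the scope of the text, so the first step is to set the provisions side by side.

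| Step in Protocol 1.5.9 | Deaths | Adjudicated non-fatal MI, heart failure, stroke, AF |
|---|---|---|
| Best-effort stripping by site staff | Yes | Yes |
| Central redaction by the DCC | Yes | Not stated |
| Sham redaction for controls | Yes | Not stated |
| LifeVest ECG barred from adjudication | Yes | Not stated |

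The parenthesis in the site-stripping sentence, which limits the removal of assignment to the VEST arm, can be read in two ways. It may mean the vest-assigned group, or the VEST component as opposed to the former PREDICTS component. On either reading, non-fatal packets get no central step and no sham step.

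**Which outcomes have a detection route as well.** For MI, heart failure and stroke the documents describe no route through vest ECG, so only masking is at issue. For AF the route is indirect:

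1. A vest participant has a shock, a qualifying alarm, or symptoms such as palpitations (1.5.5).
2. Strips go to the site, automatically or on request (1.5.5).
3. The finding, or the evaluation that follows, is entered in the medical record.
4. Medical records are a listed source for AF (Table 3), and no rule sets such findings aside.

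Controls have no counterpart to steps 1 and 2. Table 3 also has an outcome for inappropriate shocks due to SVT, so supraventricular rhythms are expected to trigger the device at times.

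**Size.** The documents give neither an AF rate nor a detection difference, so no figure can be reproduced or corrected. The following is an illustration only.

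Inputs from the documents: total sample 2300 and 2:1 allocation, so n_C = 2300/3 ≈ 767 and n_V ≈ 1533. Assumptions: no true effect on AF; control recorded-AF proportion a of 3%, 5% or 10%; relative extra recording r in the vest arm of 0 to 50%, so b = a(1 + r).

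Test: two-sided 5% pooled comparison of two proportions. With p̄ = (a + 2b)/3, s0 = √[p̄(1 − p̄)(1/n_C + 1/n_V)] and s1 = √[a(1 − a)/n_C + b(1 − b)/n_V], the rejection probability is Φ[(b − a − 1.96·s0)/s1] + Φ[(a − b − 1.96·s0)/s1].

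Worked case, a = 5% and r = 25%:

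- b = 0.0625 and p̄ = 0.0583
- s0 = 0.01037 and s1 = 0.01001
- first term Φ[(0.0125 − 0.0203)/0.01001] = Φ(−0.78) ≈ 0.217; second term below 0.001
- total ≈ 0.22, with 1533 × 0.0125 ≈ 19 extra recorded cases

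| Extra recording in vest arm (relative) | Control AF 3% | Control AF 5% | Control AF 10% |
|---|---|---|---|
| 0 | 5% | 5% | 5% |
| 10% | 6% | 8% | 11% |
| 25% | 14% | 22% | 42% |
| 50% | 40% | 63% | 93% |

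The table shows how sensitive the comparison would be to a detection difference. It is no evidence that such a difference exists.

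**The case against.** The strongest replies, and what stands of each:

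- **Masking is not missing.** Site stripping covers non-fatal packets, and it removes personal identifiers in both arms. Control packets therefore also carry removals, and a blank alone does not reveal the arm. This stands. A reader might infer that adjudicators see the assignment for these events; the documents support only weaker masking.
- **No blinding claim is broken.** The general aim of blinding adjudicators in 1.5.9 is attached to categorizing arrhythmias and deaths, and the explicit assurance concerns cause of death. This stands: the gap is one of scope and does not make a stated promise about MI, heart failure or stroke false.
- **AF detection is not built in.** The recording triggers in 1.5.4 are ventricular tachyarrhythmias and asystole, with bradyarrhythmias logged; AF is not named. Clinicians are blinded to most recordings. Table 3 does not list the LifeVest as an AF source, and 1.5.9 says that LifeVest transmissions serve outcomes analysed within the vest group. Reporting by sites is triggered by a death or a cardiovascular hospitalization, so a strip showing AF would usually have to lead to an admission before a packet exists. All this limits the route without closing it, because the exceptions to clinician blinding are the episodes most likely to reach the chart.
- **AF has little standing in the plan.** It is missing from the secondary outcomes listed in the text of 1.5.9 and from SAP B.3. The comparison rests on the Protocol Summary, Table 3 and the generic wording of 1.5.11. This stands, and is a reason not to let AF lead the point.
- **ICD/Reveal.** A reader might see this source as another uneven detector. An existing ICD is an exclusion, early implantation is expected to be rare and is permitted in both arms, and the revision log mentions Reveal only in connection with PREDICTS. The documents do not show that this source depends on the arm.

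**Conclusion.** The point holds as a limited one. For adjudicated non-fatal events, the plan specifies weaker masking than for deaths, and these events feed between-arm secondary comparisons in Protocol 1.5.11 and, for re-infarctions and hospitalizations, in SAP B.3. For AF alone there may also be a detection difference through strips released to sites. That is an inference of unknown size, and it may be zero.

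A reader might go further and infer a definite spurious excess of AF that would be read as device harm. The documents do not support this: any percentage excess only restates whatever detection difference is assumed, and the illustrative false-positive rates rest on assumed AF rates and assumed extra recording. The primary outcome is not affected by this point. The remedy is a cheap improvement to secondary comparisons.

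**What to change.** 1. In Protocol 1.5.9, extend the existing DCC redaction and sham redaction to packets for all adjudicated non-fatal cardiovascular events.
2. In the same place, state that LifeVest ECG is not to be used to adjudicate non-fatal events compared between arms. The LifeVest events in Table 3, which are described within the vest group, would not be touched.
3. Add a detection-source flag for AF to the adjudication form. Keep LifeVest-prompted cases in the main comparison, and report AF with and without them as a sensitivity analysis.

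LifeVest-prompted cases should not be dropped from the main comparison. Doing so would remove events from the vest arm only, including symptomatic AF that ordinary care would have found, while like events in controls stayed in. That could create the opposite bias. Giving both results shows how far the conclusion depends on detection.

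The cost is more redaction time at the DCC, using a procedure it already has, one added form field and a few sentences of protocol text. The primary analysis does not change.
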